10	2 weeks	5 mg		
11	2 weeks	2.5 mg		
12	During complete remission	0 mg		Restart at Step 5

Notes: On Day 1, start the oral corticosteroid regimen with an initial dosage of 60 or 80 mg/day prednisone (or equivalent), as outlined in the schedule. Increase the dose if disease activity is present after 1 week. If necessary, increase the dose again (to 240 mg/day) if disease activity is still present after the second week.

^a Disease activity is defined as the appearance of new lesions or the extension of established lesions.

^b Patients on 80 mg/d on Day 1 will start at Step 1. Patients on 60 mg/d on Day 1 will start at Step 2.

^c Patients whose disease is not controlled after increasing the corticosteroid dose to 240 mg/day will be considered to have experienced treatment failure and may receive standard-of-care treatment per the investigator's best medical judgment.

Source: Modified from Mentink LF, Mackenzie MW, Tóth GG, et al. Randomized controlled trial of adjuvant oral dexamethasone pulse therapy in pemphigus vulgaris (PEMPULS Trial). *Arch Dermatol* 2006;142:570–6.

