4.7 EFFICACY ANALYSIS

The primary and the first five ranked secondary endpoints (listed below) will be tested at an overall 5% significance level using two-sided hypothesis tests. The remaining secondary endpoints will be considered exploratory (Section 2.2.4) and not tested for significance.

To control for overall Type I error, the hypothesis testing on study endpoints will be conducted sequentially starting with the primary endpoint at 5% level of significance. If the null hypothesis relating to the primary endpoint is rejected, the first 5 secondary endpoints will then be tested in a fixed-sequence fashion in the following order:

1. Cumulative oral corticosteroid dose (prednisone or equivalent) over the treatment period
2. Total number of disease flares during the treatment period
3. Time to initial sustained complete remission
4. Time to disease flare
5. Change in health-related quality of life (HRQoL), as measured by the dermatology life quality index (DLQI) score, from baseline to Week 52

If at any step in the testing procedure, the p-value associated with a test is not <0.05, the remaining endpoints below the sequence will not be considered significant.

The mITT population will be the primary population used for the analysis of efficacy outcomes except for duration of sustained complete remission which will be on a subset

Rituximab—F. Hoffmann-La Roche Ltd
16/Statistical Analysis Plan WA29330

of mITT population (see Section 4.7.3.1). Additional analyses will be conducted for sensitivity or exploratory purposes, as described in the relevant sections below.

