4.7.2.1 Oral Corticosteroids

Oral corticosteroid exposure over the 52-week treatment period will be compared between RTX and MMF using a Wilcoxon Mann-Whitney test, assuming that the data will be non-normally distributed. If it is found that the data follows a normal distribution

Rituximab—F. Hoffmann-La Roche Ltd
19/Statistical Analysis Plan WA29330

using Shapiro-Wilk W Test, a t-test will be used to compare the difference in the two treatment groups.

Oral corticosteroid use over time will be further investigated; this includes data during the screening period. Summaries and plots will be generated, which will include:

- Mean and median daily dose per visit interval with error bars
- Total cumulative dose per visit interval
- Total number of days on oral corticosteroids over the 52-week period
- Categories of mean daily dose per visit interval (e.g., 0 mg/day, 0–<10 mg/day, ≥10 mg/day)

The mean daily dose for a given visit interval will be calculated as follows:

sum of total daily dose across all days in the visit interval ÷ (end date of visit interval – start date of visit interval + 1).

Data presented by specified visit intervals will use all available; if a patient withdraws during a time interval, no imputation will be made for the remaining days in the interval, and only available data up to the time of withdrawal will be used in the calculation. Rescue data will be included in descriptive summaries.

Additional summaries may be produced to investigate corticosteroid use for rescue patients.

A listing showing oral corticosteroid dosing for patients over the 52-week treatment period will be produced using all available data up to the exposure date, with rescue data being flagged.

Data Handling for Oral Corticosteroids

Oral corticosteroids will be recorded in the eCRF under the concomitant medications page. Dose modifications will be tracked by entering the start and stop dates for each dose received. Medications will be flagged as oral corticosteroids using the Sponsor's corticosteroid drug basket and the route administered information as recorded on the eCRF. The Sponsor will review the concomitant medications data on an ongoing basis to ensure medications are being correctly recorded, and are being flagged as appropriate.

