4.7.2.2 Total Number of Flares

The total number of flares occurring during the treatment period will be evaluated by taking into account the number of flares experienced and the exposure period. Patient level flare and exposure data will then be aggregated, and the rate of flares compared between the RTX and MMF treatment groups. Rate of flare will be analyzed using a Poisson regression model with a log link and the log of each patient's duration in study as an offset variable. The model will include factors for treatment, region, duration of illness, baseline PDAI activity score, and baseline prednisone dose. The total number of flares, total exposure (weeks), and rate of flare will be presented by treatment group along with maximum likelihood estimates for the rate ratio, 95% confidence interval for the rate ratio, and p-value. A Pearson Chi-Square test will be used to assess over-dispersion of Poisson model. If an over-dispersion is detected based on this test, then a negative binomial model will be used. If the number of flares has an excess of zero counts according to the score test ([van den Broek, 1995](#)), a zero-inflated negative binomial model will be applied.

The exposure period for a patient will be the duration from Day 1 to the earliest of the following: early withdrawal, receipt of rescue, Week 52 visit.

Additional exploratory work may be undertaken to investigate the potential changes of flare rates over time, for example by assessing the number of flares over specified time intervals.

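### Cumulative oral corticosteroid dose, the first gated secondary, is tested without the randomisation strata or Day 1 prednisone dose, and an under-specified normality check chooses the test

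*SAP*

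**What the plan says.** SAP 4.7 sets the confirmatory framework. The primary and five ranked secondaries "will be tested at an overall 5% significance level using two-sided hypothesis tests". If the primary succeeds, "the first 5 secondary endpoints will then be tested in a fixed-sequence fashion in the following order", and the first in that order is "Cumulative oral corticosteroid dose (prednisone or equivalent) over the treatment period". Once a step fails, "the remaining endpoints below the sequence will not be considered significant".

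SAP 4.7.2.1 gives the test for this first step: "Oral corticosteroid exposure over the 52-week treatment period will be compared between RTX and MMF using a Wilcoxon Mann-Whitney test". It names no stratum and no covariate. It then adds a conditional switch: if the data are found to be normal "using Shapiro-Wilk W Test, a t-test will be used to compare the difference in the two treatment groups". It names no effect estimate or confidence interval for the comparison.

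The adjacent endpoint, number of flares (SAP 4.7.2.2), is handled differently: "The model will include factors for treatment, region, duration of illness, baseline PDAI activity score, and baseline prednisone dose".

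On starting dose, the footnote to Table 1 in Protocol 3.1.2 reads: "Patients on 80 mg/d on Day 1 will start at Step 1. Patients on 60 mg/d on Day 1 will start at Step 2". Each of those two steps lasts one week.

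**The concern.** Three features sit together on the endpoint that gates flares, time to remission, time to flare and DLQI.

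- **Strata.** Randomisation is stratified by region and duration of illness (SAP 3.1). The analysis of this endpoint ignores both factors.
- **Day 1 dose.** This is a baseline variable and also a component of the outcome, because an 80 mg starter enters the taper one step earlier. The SAP adjusts for it in the flare model, lists it as a possible covariate for the primary (4.7.1.6) and uses it as a subgroup factor (4.7.4). It is left out of the one endpoint that sums the doses.
- **Choice of test.** Wilcoxon or t-test depends on a pre-test that is not fully defined, and the two tests answer different questions.

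At stake is some power at the first gate, and whether two analysts following the text would report the same test.

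**Working it through.** **1. Adjustment across the confirmatory tests (SAP 4.7.1 to 4.7.2.5)**

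| Order | Endpoint | Method | Strata used | Day 1 dose used |
|---|---|---|---|---|
| Primary | Sustained complete remission | CMH | Yes | No |
| 1 | Cumulative steroid dose | Wilcoxon, or t-test | **No** | **No** |
| 2 | Flares | Poisson regression | Yes | Yes |
| 3 | Time to remission | Stratified log-rank | Yes | No |
| 4 | Time to flare | Stratified log-rank | Yes | No |
| 5 | DLQI | Repeated measures | Yes | No |

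**2. The plan's own power figure.** The SAP states power only for the primary: 61 per arm, 65% vs 40%, two-sided 5%. The pooled chi-squared formula gives 79.7%, which agrees with the stated value of about 80%. There is no such figure for steroid dose.

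**3. Starting dose under Table 1, no step back**
- From 60 mg: 60×7 + 40×7 + 14×(30+20+15+12.5+10+7.5+5+2.5) = 420 + 280 + 1,435 = 2,135 mg over 18 weeks.
- From 80 mg: 80×7 + 2,135 = 2,695 mg over 19 weeks.
- Difference: 560 mg, which is 560/2,135 = 26% of the lower total.

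**4. Variance formula.** Let s be the share starting at 80 mg. The share of variance explained is R² = 560²·s(1−s)/SD². If the unadjusted test has 80% power, adjusted power is Φ((1.960+0.842)/√(1−R²) − 1.960). Both s and SD are assumed. For s = 0.5:

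| SD (mg) | R² | Adjusted power |
|---|---|---|
| 700 | 0.160 | 86.4% |
| 1,000 | 0.078 | 83.1% |
| 1,500 | 0.035 | 81.4% |
| 2,000 | 0.020 | 80.8% |
| 3,000 | 0.009 | 80.3% |

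With s = 0.2 the gain runs from 0.2 to 4.1 points over the same SDs.

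**5. Simulation of the Table 1 taper.** 61 per arm, 400 runs per row, Monte Carlo error about 2.5 points. The weekly chance of disease activity is assumed, varies between patients and is lower at 0 mg. Rank ANCOVA adjusts for Day 1 dose and one binary stratum; van Elteren stratifies by the same two. Half start at 80 mg unless noted.

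| Weekly rate, MMF / rituximab | SD (mg) | Wilcoxon | Rank ANCOVA | van Elteren |
|---|---|---|---|---|
| 2% / 0.8% | 931 | 0.435 | 0.600 | 0.492 |
| 3% / 1.5% | 1,330 | 0.398 | 0.468 | 0.442 |
| 5% / 2.5% | 2,210 | 0.592 | 0.650 | 0.590 |
| 5% / 2.5%, 20% start at 80 mg | 2,219 | 0.630 | 0.662 | 0.638 |
| 5% / 2.5%, prognostic stratum | 2,774 | 0.485 | 0.618 | 0.580 |
| 10% / 5.5% | 5,029 | 0.678 | 0.665 | 0.640 |

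The largest gain is 0.600 − 0.435, about 16 points, when flares are few. When flares dominate the total there is no gain. With equal rates (3% in both arms), rejection was 0.05 for Wilcoxon and for rank ANCOVA.

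**6. The normality switch.** 61 per arm, 8,000 runs, Shapiro-Wilk on the pooled data at 5% (both choices assumed, since the SAP gives neither).

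| Data | Wilcoxon power | t-test power | Switch power | Switch type I error |
|---|---|---|---|---|
| Normal | 0.781 | 0.800 | 0.799 | 0.052 |
| Lognormal, sigma 0.3 | 0.776 | 0.779 | 0.775 | 0.048 |

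In every taper scenario Shapiro-Wilk rejected normality, so the planned procedure was simply the Wilcoxon test.

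**The case against.** The strongest reply is that nothing here is invalid. The unadjusted Wilcoxon test holds its level, chance imbalance in starting dose is already covered by that level, and region and duration of illness are balanced by stratified blocks. Baseline prednisone dose is also tabulated (SAP 4.4.2), so an imbalance would be seen. All of this stands: the issue is efficiency and pre-specification.

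It can also be said that post-randomisation dosing swamps the starting dose. By Table 1, one restart at Step 5 adds 14×(20+15+12.5+10+7.5+5+2.5) = 1,015 mg, and a pass through Steps A, B and A adds 840+1,680+840 = 3,360 mg. That is fair, and it is why the gain vanishes in the highest-flare scenario. It does not make adjustment harmful there: 0.678 vs 0.665 is within Monte Carlo error.

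A reader might infer three stronger things that the documents do not support:
- **That Day 1 dose fixes 560 mg of the total.** Protocol 3.1.2 presents Table 1 as a guideline open to physician and local practice, and a 60 mg starter with disease activity is sent to Step 1, so that patient also takes an 80 mg week.
- **That the normality switch itself loses power.** The check in the working found no measurable loss against the named Wilcoxon test.
- **That the test is chosen after unblinding.** SAP 4.7.2.1 does not say when, or on which data, Shapiro-Wilk is run.

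**Conclusion.** The point holds as one of efficiency and pre-specification. The gatekeeping secondary is the only confirmatory test without the randomisation strata, and it leaves out a baseline dose that the next test uses. Adjustment would gain about 0 to 6 points of power by the variance formula (SD 700 to 3,000 mg, 20% to 50% starting at 80 mg, 80% power unadjusted). It would gain up to about 16 points in a low-flare simulation, and nothing when flares dominate the total dose. No single figure can be claimed: SD, effect size and the 60/80 split are all absent from the documents, and a double-digit loss should be read as one end of an assumed range.

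The switch is a separate fault. Its significance level is missing, as is whether pooled data, each arm or residuals are tested, so the reported test and effect measure depend on the data. Failing to reject normality is also not evidence of normality.

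**What to change.** In SAP 4.7.2.1:
1. Delete the Shapiro-Wilk and t-test branch.
2. Name one test: rank analysis of covariance of cumulative dose, with region, duration of illness and Day 1 prednisone dose (60 or 80 mg) as covariates.
3. If a stratified rank test is preferred, use van Elteren stratified by region and duration of illness. Crossing these with Day 1 dose gives 2×2×2 = 8 cells for about 122 patients, about 15 per cell on average and some likely sparse. Van Elteren also gained less than rank ANCOVA in the simulations.
4. State the effect estimate and its confidence interval. Use one that carries the same adjustment, or report a Hodges-Lehmann shift labelled as unadjusted.

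The cost is SAP wording and a few lines of code before database lock. All three covariates are already collected and used in SAP 4.7.2.2. Sample size, visits and the testing order do not change.

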2.1.2 Secondary Efficacy Objectives

The secondary efficacy objectives for this study are as follows:

- To evaluate the efficacy of rituximab compared with MMF, as measured by the time to disease flare, the duration of sustained complete remission, the total number of disease flares during the treatment period, and the time to initial sustained complete remission

Rituximab—F. Hoffmann-La Roche Ltd
28/Protocol WA29330, Version 5

- To assess corticosteroid exposure over 52 weeks
- To assess the effect of rituximab compared with MMF on health-related quality of life (HRQoL), as measured by the Dermatology Life Quality Index (DLQI)
- To assess the effect of rituximab compared with MMF on patients' impression of PV symptoms, as measured by the Patient Global Impression of Change (PGIC) questionnaire
- To assess the effect of rituximab compared with MMF on clinician impression of patients' PV symptoms, as measured by the Clinician Global Impression of Change (CGIC) questionnaire

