3.4 OUTCOME MEASURES

3.4.1 Efficacy Outcome Measures

3.4.1.1 Primary Efficacy Outcome Measure

The primary efficacy outcome measure is as follows:

- Proportion of patients (*excluding TM patients*) who achieve a sustained complete remission without experiencing an event that constitutes treatment failure (as defined in Section 3.1.3), as measured at Week 52

Sustained complete remission is defined as achieving healing of lesions with no new active lesions (i.e., PDAI activity score of 0) while on 0 mg/day prednisone or equivalent, and maintaining this response for a total of at least 16 consecutive weeks, during the 52-week treatment period.

Patients with transient new lesions for 1 week or less that heal without additional systemic corticosteroid therapy will not be considered to have experienced treatment failure.

Rituximab—F. Hoffmann-La Roche Ltd
39/Protocol WA29330, Version 5

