4.3.2 Dosage, Administration, and Compliance

4.3.2.1 Rituximab and Rituximab Placebo

Rituximab at a dose of 1000 mg (or matching placebo) will be administered by IV infusion on Day 1 and Day 15, with repeat rituximab (or matching placebo) administration on Day 168 and Day 182 provided specific safety criteria have been met (see Section 4.6.4). Rituximab (and matching placebo) should be administered in a

Rituximab—F. Hoffmann-La Roche Ltd
45/Protocol WA29330, Version 5

hospital, clinic, or healthcare-related environment where full resuscitation facilities are immediately available and under the close supervision of an experienced healthcare professional.

After the end of the infusion, the IV line should remain in place for at least 1 hour to enable administration of drugs intravenously, if necessary. If no adverse events occur during this period of time, the IV line may be removed. Rituximab should not be administered in the setting of an active infection.

All patients will receive 100-mg IV methylprednisolone (patients in the rituximab arm) or a saline solution (patients in the rituximab placebo arm) by slow infusion, to be completed at least 30 minutes prior to each infusion of rituximab or rituximab placebo, respectively. All patients should be premedicated with paracetamol/acetaminophen (1 g PO) and an antihistamine (diphenhydramine HCl 50 mg PO [or IV equivalent] or equivalent dose of a similar agent, or in accordance with local approved labeling) 30 to 60 minutes prior to the start of a rituximab infusion.

Detailed guidance for the administration of rituximab, including the rates of infusions and the actions to be taken in the event of an infusion-related reaction, is provided in [Appendix 3](#).

Guidelines for dosage modification and treatment interruption or discontinuation are provided in Section 4.6.4, Section 5.1.1.9, and [Appendix 3](#).

Any overdose or incorrect administration of rituximab should be noted on the Study Drug Administration eCRF. Adverse events associated with an overdose or incorrect administration of rituximab should be recorded on the Adverse Event eCRF.

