2.3 DETERMINATION OF SAMPLE SIZE

The primary efficacy endpoint of this study is the proportion of patients (excluding TM patients) achieving a sustained complete remission, as assessed at Week 52, that has been maintained for ≥ 16 consecutive weeks during the 52-week treatment period. With use of limited data available in the literature from randomized clinical trials of MMF and investigator-initiated trials of rituximab ([Beissert et al. 2010](#)), it is estimated that approximately 40% of patients with PV receiving MMF will achieve a sustained complete remission. It is estimated that patients receiving rituximab will induce a sustained complete remission rate of 65%. On the basis of these assumptions, a total of 122 patients randomized to either the rituximab arm or the MMF arm in a 1:1 ratio (61 patients in the rituximab arm and 61 patients in the MMF arm) will yield approximately 80% power in a two-sided test at the 5% significance level. To account for the 10 TM patients excluded from the primary efficacy analysis, approximately 132 patients will be randomized in total. The sample size calculation was performed using nQuery Advisor 7 using the two-group chi-squared test of equal proportions. The primary analysis method using a Cochran-Mantel-Haenszel test adjusting for stratification factors is expected to provide at least 80% power to detect the difference in proportions.

Rituximab—F. Hoffmann-La Roche Ltd
8/Statistical Analysis Plan WA29330

No adjustment will be made for dropouts. Patients withdrawing early from the study or meeting the criteria for treatment failure (including rescue therapy) will be assessed based on available data up until the point of withdrawal or treatment failure only for the primary endpoint. Patients with missing or incomplete data where a status cannot be determined after applying relevant imputation rules will be set to non-responders.

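### The first ranked secondary endpoint counts oral corticosteroid only, so up to 4 x 100 mg IV methylprednisolone given by design to the rituximab arm alone is left out, and no planned analysis adds it back

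*SAP*

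**What the plan says.** Protocol 4.3.2.1 makes the steroid premedication differ by arm: "All patients will receive 100-mg IV methylprednisolone (patients in the rituximab arm) or a saline solution (patients in the rituximab placebo arm". Infusions are scheduled on Days 1, 15, 168 and 182. The last two depend on safety criteria, and Protocol 3.1.1 drops them for patients given rescue rituximab between Weeks 12 and 24.

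SAP 4.7 places cumulative oral corticosteroid dose first in the fixed sequence after the primary endpoint; the sequence "will be tested at an overall 5% significance level using two-sided hypothesis tests". SAP 4.7.2.1 identifies oral corticosteroids from the sponsor's "corticosteroid drug basket and the route administered information as recorded on the eCRF" and converts only those oral entries to prednisone equivalents. SAP 4.7.1.3 sends the steroid component of the primary endpoint to the same rules. The sensitivity analyses in SAP 4.7.1.5 cover relaxed treatment-failure criteria, a tipping point for withdrawals, and inclusion of telemedicine patients. None of them concerns IV steroid.

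The objective behind the secondary endpoint names no route: "To assess corticosteroid exposure over 52 weeks" (Protocol 2.1.2). Nor does the primary definition, which requires a PDAI activity score of 0 "while on 0 mg/day prednisone or equivalent, and maintaining this response for a total of at least 16 consecutive weeks" (Protocol 3.4.1.1).

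**The concern.** An oral-only total compares arms fairly when non-oral steroid is balanced between them. Here the protocol guarantees that it is not. Part of any apparent steroid saving on rituximab would then be steroid moved from the oral to the IV route. Because this test opens the rest of the sequence, a result helped by the omission also affects whether the later secondary endpoints are tested.

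There is a second, narrower question. The Day 168 and Day 182 doses fall at and after the point (Week 24) by which oral steroid should have reached 0 mg/day. The documents do not say whether a premedication day is a 0 mg/day day. The answer bears on the primary endpoint and on time to sustained complete remission, the third ranked secondary.

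**Working it through.** **Inputs from the documents.** 61 patients per arm; response 40% against 65%; two-sided 5%; no dropout allowance (SAP 2.3). Taper steps (Protocol Table 1, repeated in SAP Appendix 4). Premedication 100 mg per active infusion, at most four (Protocol 4.3.2.1).

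**Inputs assumed.** Methylprednisolone-to-prednisone factor 1.0 to 1.25. Log-normal cumulative exposure with mean 4000-5000 mg and coefficient of variation (CV) 0.3-0.7. The documents give none of these.

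**1. The plan's own figure.** SAP 2.3 states "approximately 80% power in a two-sided test at the 5% significance level". With a pooled rate of 0.525:

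z = [0.25 x sqrt(61) - 1.96 x sqrt(2 x 0.525 x 0.475)] / sqrt(0.40 x 0.60 + 0.65 x 0.35) = (1.953 - 1.384) / 0.684 = 0.83, so power is 79.7%.

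The stated power reproduces.

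**2. Uncounted dose.** 4 x 100 = 400 mg methylprednisolone, which is 400 mg (factor 1.0) to 500 mg (factor 1.25) prednisone equivalent in the rituximab arm and 0 mg in the MMF arm. With two infusions only, it is 200-250 mg.

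**3. Against an uninterrupted taper.**
- 60 mg start: 7 x (60 + 40) + 14 x (30 + 20 + 15 + 12.5 + 10 + 7.5 + 5 + 2.5) = 700 + 1435 = 2135 mg over 126 days.
- 80 mg start: 2135 + 7 x 80 = 2695 mg over 133 days.
- 400/2695 = 14.8%; 500/2695 = 18.6%; 400/2135 = 18.7%; 500/2135 = 23.4%.

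Patients who flare take more. Against an assumed mean of 4000-5000 mg the share is 400/5000 = 8% to 500/4000 = 12.5%.

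**4. What the shift could do to the ranked test.** Simulation with 61 per arm, equal total systemic dose in both arms, the rituximab arm's counted dose lowered by the uncounted amount, and the Wilcoxon test. The table gives the share of trials favouring rituximab at p<0.05.

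| Uncounted dose | Share of trials |
|---|---|
| 500 mg | 67% (mean 4000, CV 0.3); 39% (4000, 0.5); 25% (5000, 0.5); 29% (4000, 0.7) |
| 400 mg | roughly 19-49% |
| 200-250 mg | about 7-24% |
| none | about 2.5% |

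**5. Primary endpoint.** On an uninterrupted taper the first 0 mg day is Day 127 (60 mg start) or Day 134 (80 mg start). A 112-day run from there ends on Day 127 + 111 = 238 or Day 134 + 111 = 245, so it spans Days 168 and 182. If those days counted as non-zero, a new run could begin on Day 183 and would qualify on Day 183 + 111 = 294. From Day 183 to Day 364 there are 182 days, so a patient who stays in remission to Week 52 still qualifies. Only runs that start before Day 183 and end before about Day 294 change status.

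SAP 4.7.1.2 dates loss of PDAI 0 at the visit where it is seen, and PDAI visits after Day 168 are Days 224, 280, 336 and 364. At scheduled visits, PDAI loss therefore matters only if seen at about Day 280 in a run begun by about Day 280 - 112 = 168. Steroid restart, treatment failure or withdrawal before Day 294 are the other ways.

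**6. Time to sustained remission.** For a rituximab patient already in remission, the start date would move to Day 183, by up to 183 - 127 = 56 days on an uninterrupted taper.

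**The case against.** The strongest reply is that the SAP does what the protocol asks. Protocol 3.4.1.2 and 6.5.2 both name the endpoint as cumulative oral dose, and selecting by route carries that out. A reader might infer that the SAP departs from the protocol, or that the ranked endpoint must be replaced. The documents support neither. The gap lies between a protocol-defined endpoint and the broader objective it serves.

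A reader might also infer that premedication breaks the 0 mg/day condition and so undermines the primary endpoint. Protocol 3.1.2 speaks of tapering oral corticosteroids to 0 mg/day by Week 24 and holding them there, while the same protocol schedules methylprednisolone on Days 168 and 182. The two fit together if 0 mg/day means the oral background taper, and SAP 4.7.1.3 reads it so. What stands is that no sentence says this, and that the number of patients affected is small but unquantified.

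The simulated rates should not be read as the plan's rate of false steroid-sparing claims. The upper figures give every rituximab patient all four doses at factor 1.25, the mean and CV are undocumented, and the ranked test is run only after the primary succeeds, which the simulation ignores.

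It is tempting to add that corticosteroid-related adverse events will be set against an understated exposure. SAP 4.9.2 lists those events but names no exposure variable, so this cannot be shown.

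Finally, the premedication dose is fixed and disclosed, and infusion counts are summarised (SAP 4.3 and 4.9.1), so a reader of the report could bound the difference. That helps, but it does not replace a planned analysis.

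**Conclusion.** The concern holds for the first ranked secondary endpoint. By design it omits up to 400-500 mg prednisone equivalent per patient in the rituximab arm and nothing in the MMF arm, and the error runs in one direction only. Four doses is the scheduled maximum, so the average omission will be smaller where the Day 168 and Day 182 infusions are not given. The 15-23% share rests on the assumed conversion factor and an uninterrupted taper; the 8-12.5% share rests on the same factor and an assumed mean. The simulation shows that the shift is large enough to matter to a Wilcoxon test with 61 per arm, but does not fix a probability.

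For the primary endpoint the point is one of definition with limited reach: remissions begun before Day 183 and lost before about Day 294. For time to sustained remission the reach is wider, because start dates would move for patients who remain responders.

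**What to change.** - **SAP 4.7.2.1.** Keep cumulative oral dose as the ranked endpoint. Add a required supportive analysis of total systemic dose (oral plus IV premedication) in prednisone equivalents, counting 100 mg methylprednisolone for each active infusion received, and state the conversion factor. Any claim of lower overall corticosteroid exposure should rest on this analysis.
- **SAP 4.7.1.3.** State whether protocol premedication counts toward 0 mg/day.
- **SAP 4.7.1.5.** Add a sensitivity analysis of the primary and time-to-sustained-remission endpoints that treats premedication days as non-zero.

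The cost is SAP wording and one derived variable from infusion and premedication records. The steroid-sparing difference may come out somewhat smaller. No change to the premedication is proposed.
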